6.1.5 Efficacy evaluation

6.1.5.1 Primary efficacy analysis

There will be three primary variables in the study:

- Time to progression to diabetes (on a discrete time scale)
- Time to first extended cardiovascular endpoint after randomization (in days since randomization)
- Time to first core cardiovascular endpoint after randomization (in days since randomization)

These variables will be analyzed using a closed testing procedure for each drug. The three endpoints will be tested in a parallel manner for each drug (Table 6). There will be unequal weights for tests of the progression to diabetes and the cardiovascular endpoints.

Due to the discrete nature in which time to diagnosis of diabetes is measured (every six months for fasting glucose from visits 6-11, every twelve months for post-prandial glucose), a score test will be used based on a discrete time proportional odds model (Cox's [16] model for discrete time data, discussed also in [17]) for the effect of nateglinide (valsartan) stratified for valsartan (nateglinide) and history of cardiovascular disease at baseline (yes/no – see section 3.3.2 for a definition). This model is analogous to TIES = DISCRETE in the SAS® procedure PHREG.

For the first three years in study the time intervals used in the model will be defined by the six-monthly study visit period of the visit at which it was detected (in line with the definition of progression to diabetes (Section 3.5.3), a confirmatory measurement has to take place at a repeat visit). If progression was detected at an unscheduled visit (or defined by the diabetes adjudication process), it will be assigned to the next regular six-monthly visit. After three years FPG/OGTT assessment intervals are yearly.

For the endpoints 'time to first extended/core cardiovascular event', the effect of nateglinide (valsartan) will be tested using a logrank statistic, stratified for valsartan (nateglinide) and for history of cardiovascular disease at baseline (yes/no). That is, a score test will be implemented, with TIES = EXACT in the SAS® procedure PHREG. If not otherwise stated, all efficacy analyses will be performed on the ITT population.

Progression to diabetes and cardiovascular endpoints are defined as in Section 3.5.3 of the protocol.

The six null hypotheses will be:

- N1 There is no difference between the nateglinide and non-nateglinide treated groups in time to progression to diabetes.

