- N2 There is no difference between the nateglinide and non-nateglinide treated groups in time to first extended cardiovascular endpoint.
- N3 There is no difference between the nateglinide and non-nateglinide treated groups in time to first core cardiovascular endpoint.
- V1 There is no difference between the valsartan and non-valsartan treated groups in time to progression to diabetes.
- V2 There is no difference between the valsartan and non-valsartan treated groups in time to first extended cardiovascular endpoint.
- V3 There is no difference between the valsartan and non-valsartan treated groups in time to first core cardiovascular endpoint.

Testing will be done using the closed testing procedure described in Section 6.1, Table 6, using a 2.5% one-sided alpha level. Nateglinide or valsartan will be declared superior to non-nateglinide/non-valsartan for a primary endpoint if the respective intersection hypotheses (see Table 6) can be rejected in favor of the experimental drug using the adjustment criteria as specified in Section 6.1.7 "Interim analyses".

The interaction effect of nateglinide and valsartan will be tested in separate models that include an interaction term. For the progression to diabetes, this will be done by a discrete time proportional odds model. For the cardiovascular endpoints, a standard Cox models (on a continuous time scale) will be applied, using a TIES=EXACT option in SAS. In each of these

models, the two treatment effects, and history of cardiovascular disease at baseline will be fitted as covariates, in addition to the interaction term.

Two-sided 95% confidence intervals of the hazard ratio will be presented for each of the primary comparisons.

This factorial trial is testing two drugs, and therefore can be considered a combination of two trials into one. The combined type I error probability of two independent trials (one for each drug, each using 5% alpha-level) is 9.75%. As the overall type I error of this trial will be exactly the same, a 5% alpha-level will be used for each of the two experimental treatments.

The primary analysis will be on the ITT population, but the models will also be performed as supportive analysis for the per-protocol population.

Confidence intervals will be calculated for the hazard ratio in two-group treatment comparisons of the two monotherapies vs. placebo, combination therapy vs. placebo, and combination therapy vs. the two monotherapies.

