For the glycemic primary endpoint, it is assumed that 6% of the placebo IGT patients will progress to diabetes each year. This assumption was obtained using progression rates observed in recently reported studies [20,21] and considering the existence of lifestyle advice as background therapy for all patients in NAVIGATOR. Treatment effects were expected to be 25% reduction in the hazard for progression to diabetes in each monotherapy group (nateglinide or valsartan) and 39.1% reduction in the nateglinide-valsartan combination group (consistent with the “75% additivity” approach as used for the cardiovascular endpoint). Using the same expectations for the effect of treatment discontinuation as for the cardiovascular outcome, there will be greater than 99% testwise power to detect a treatment difference in time to progression to diabetes.

These power calculations, and the calculation of 1374 patients with extended cardiovascular endpoints at the end of the trial, were performed using a generic SAS program, which was crosschecked against the results obtained from nQuery advisor® version 4.1 (for the extreme cases, and by use of approximate “average” hazards for the pooled groups over the whole trial) and against simulation results.

Table 7 shows the effects of the changes to the testing procedure on power under the protocol assumptions about treatment effects. However, the closed testing procedure would provide a more robust performance under scenarios in which the effect size for the extended CV endpoint is smaller and the effect size is as large or larger for the core CV endpoint.

Table 7 Power comparison between hierarchical and closed testing procedure (based on 10,000 simulations)

Assumed hazard reduction			Test procedure	Power				
Progression to diabetes	Core CV endpoint	Extended CV endpoint		Progression to diabetes	Any endpoint significant	Extended CV endpoint	Core CV endpoint	Any CV endpoint significant
20%	16%	16%	Hierarchical	90.0%	90.0%	90.0%	NA	90.0%
			Closed	>99.9%	>99.9%	85.8%	67.1%	86.6%

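### The only model named for the diabetes endpoint estimates a per-interval odds ratio, but the effect is to be reported as a hazard ratio; the difference is small and leaves the test untouched

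*Protocol*

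**What the plan says.** Protocol section 6.1.5.1 sets the analysis of time to diabetes: "a score test will be used based on a discrete time proportional odds model". It gives the software form: "This model is analogous to TIES = DISCRETE in the SAS" procedure PHREG. The same model is named again for the diabetes interaction test. No other model is named for this endpoint.

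On the time grid, for the first three years "the time intervals used in the model will be defined by the six-monthly study visit period". The text then adds: "After three years FPG/OGTT assessment intervals are yearly".

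On reporting, the section says: "Two-sided 95% confidence intervals of the hazard ratio will be presented for each of the primary comparisons". Diabetes is one of the three primary variables. The label returns for the pairwise comparisons: "Confidence intervals will be calculated for the hazard ratio in two-group treatment comparisons of the two monotherapies vs. placebo". Nowhere is the diabetes estimate called an odds ratio.

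Section 6.2 plans on the hazard scale: "Treatment effects were expected to be 25% reduction in the hazard for progression to diabetes in each monotherapy group". The control rate is given as: "it is assumed that 6% of the placebo IGT patients will progress to diabetes each year".

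**The concern.** TIES=DISCRETE fits a logistic model to the conditional probability of progressing within an interval, among those still free of diabetes at its start. The exponentiated coefficient is an odds ratio. It equals the hazard ratio only in the limit of very short intervals or very rare events.

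Two consequences follow. First, a reader who compares the reported hazard ratio with the planned 0.75 would be comparing different quantities. Second, if the hazard ratio is constant, the per-interval odds ratio depends on interval width. A grid that moves from 6 to 12 months would then have no single odds ratio, and the fitted value would be a mixture over the two widths.

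Diabetes develops in continuous time and is only detected at visits. The matching model is grouped proportional hazards with a complementary log-log link, whose coefficient is the log hazard ratio at any interval width.

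The hazard-ratio label is right for the two cardiovascular endpoints, which use a logrank test and Cox models. The mismatch concerns diabetes only.

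**Working it through.** **Inputs.** From section 6.2: placebo progression 6% per year, hazard ratio (HR) 0.75 per monotherapy, 9152 patients, and the stated discontinuation and follow-up assumptions. From section 6.1.5.1: 6-month model intervals to year 3. From section 3.1: projected duration about 8 years. Assumed: yearly model intervals after year 3, a constant hazard, and rates of 10% and 15% per year to show the range.

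**Step 1: reproduce the plan's figures.**
- Combination effect with 75% additivity: full independence gives 1 − 0.75² = 0.4375; 0.25 + 0.75 × (0.4375 − 0.25) = 0.3906, which matches the stated 39.1%.
- Diabetes power: the section 6.2 assumptions (18 months' accrual, 4.25 further years, 30% discontinuation over five years with a quarter of the effect kept, 25% of discontinuers not followed) give about 1918 events and an average HR of 0.801. Power = Φ(√1918/2 × |ln 0.801| − 1.96) = 99.8%, in line with the stated figure above 99%.
- Cardiovascular cross-check: 1374 events at HR 0.84 gives 89.8%, against the stated 90%.

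**Step 2: odds ratio in one interval.** With annual risk r, hazard λ = −ln(1 − r) and width w in years, the odds of progressing are exp(λw) − 1 on control and exp(λ·HR·w) − 1 on treatment. So

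OR(w) = [exp(λ·HR·w) − 1] / [exp(λw) − 1].

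For r = 0.06, λ = 0.0619:
- w = 0.5: 0.02348 / 0.03142 = 0.747
- w = 1: 0.04750 / 0.06383 = 0.744

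**Step 3: pool over the grid.** A large-sample logistic fit with a separate baseline for each interval (six 6-month intervals, then yearly to year 8) gives the value that TIES=DISCRETE would approach. All rows have true HR 0.75:

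| Placebo rate per year | 6-month OR | 12-month OR | Pooled, 8 years |
|---|---|---|---|
| 6% (protocol) | 0.7471 | 0.7442 | 0.7454 |
| 10% (assumed) | 0.7450 | 0.7400 | 0.7424 |
| 15% (assumed) | 0.7423 | 0.7346 | 0.7387 |

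If the grid stayed six-monthly throughout, the pooled value at 6% would be 0.7471. A complementary log-log fit to the same grouped data returns 0.7500 at either width.

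**Step 4: size against sampling error.** At 6%, ln(0.7454/0.75) = −0.006. The standard error of the log effect with 1918 events is about 2/√1918 = 0.046. The shift is 0.006/0.046, about 13% of one standard error. At an assumed 15% the gap is 0.75 − 0.7346 = 0.015 in a 12-month interval and 0.75 − 0.7387 = 0.011 pooled.

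**Step 5: direction and null.** For a harmful effect, HR = 1/0.75 = 1.333 at 6% per year, the OR is 1.340 (6-month) and 1.347 (12-month): again further from 1. If HR = 1, OR(w) = 1 at every width, so the two null hypotheses are the same.

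**The case against.** **The link between test and interval is inferred.** Section 6.1.5.1 specifies a score test and, separately, promises intervals for the hazard ratio. It does not say that the diabetes interval comes from the discrete model, and the SAP, not available here, could name another. This stands in part. But the protocol fixes a model and a label that disagree and names no second model, so the point can be raised on its own text.

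**The yearly model grid is not stated.** This stands. Model intervals are defined only to year 3. The yearly sentence concerns assessments, and unscheduled or adjudicated cases go to the next six-monthly visit. The dependence on width is general, but the change of width within this trial's model is an implication.

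**The hazard ratio is not constant either.** Under the planning assumptions, a monotherapy effect of 0.75 drifts by year 5 to about 0.70 × 0.75 + 0.30 × 0.9375 = 0.806, where 0.9375 = 1 − 0.25 × 0.25. That drift of about 0.056 is far larger than the gap of about 0.005 between odds ratio and hazard ratio. This stands: a complementary log-log estimate would then be an average hazard ratio. It would still be on the scale that the protocol names.

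**Stronger readings to avoid.** A reader might infer that the reported effect is biased in favour of the drugs. The odds ratio lies further from 1 in both directions, so a harmful effect would look worse. A reader might also infer that the primary test is invalid; Step 5 shows that it is not.

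**Conclusion.** The point holds as a small error of estimand and label. For diabetes, the protocol attaches a hazard-ratio label to a model that estimates a per-interval odds ratio. At its own planning values the pooled estimate would be about 0.745 instead of 0.750. At assumed rates up to 15% per year the gap reaches at most about 1.5 percentage points, in a 12-month interval. These figures rest on a constant hazard and a constant hazard ratio, and the pooled ones also on a yearly model grid after year 3.

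The score test, type I error and closed testing procedure are unaffected. The documents do not support calling this a material bias. What needs correcting is that the primary diabetes estimate should be what its label says, on the scale on which it was planned.

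**What to change.** 1. Keep the pre-specified score test unchanged. An efficacy interim analysis has already been performed, and nothing here calls for a new primary test.
2. Estimate the diabetes effect and its 95% interval from a grouped proportional-hazards model (complementary log-log link, interval-specific baseline, same intervals and stratification). Report it as the hazard ratio, described as an average if the effect changes over time. Do the same for the pairwise comparisons.
3. At minimum, label the TIES=DISCRETE estimate an odds ratio per interval.
4. State the model interval grid after year 3, including where unscheduled and adjudicated cases fall on it.

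The cost is one model statement and one sentence on the grid, settled before unblinding. No data, power or alpha is lost. The downside is that test and interval would come from different models and could disagree in a borderline case, so the plan should say that the score test decides significance.

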6.1.5.2 Exploratory efficacy analyses

The following additional exploratory analyses will be performed:

- Time to first occurrence of each of the individual components of the extended cardiovascular endpoint
- Time to all cause death
- Time to first cardiovascular-related hospitalization
- Time to first extended CV endpoint including suspected events which were not Committee-confirmed, i.e., including investigator reports of cardiovascular death, non-fatal myocardial infarction, non-fatal stroke, revascularization procedure, hospitalization for congestive heart failure, or hospitalization for unstable angina which were not confirmed by the Cardiovascular Adjudication Committee
- Time to first core CV endpoint including suspected events which were not Committee-confirmed, i.e., including investigator reports of cardiovascular death, non-fatal myocardial infarction, non-fatal stroke, or hospitalization for congestive heart failure which were not confirmed by the Cardiovascular Adjudication Committee

A logrank test, set up in the same way as for the primary cardiovascular endpoint, will be performed for these analyses.

Additional exploratory analyses for renal function will be performed using a discrete time proportional odds model (the same method employed for the primary endpoint of diabetes progression):

- Time to development of microalbuminuria (for subjects without albuminuria at baseline; microalbuminuria is defined as urine albumin/creatinine ratio > 30 mg/g, confirmed by a second measurement)
- Time to progression from microalbuminuria at baseline to macroalbuminuria (urine albumin/creatinine ratio > 300 mg/g, confirmed by a second measurement)
- Time to two-fold increase from baseline in serum creatinine (confirmed by a second measurement), endstage renal disease (renal transplant, dialysis), or renal death

Confirmatory measurements for renal function related variables must take place within one year after the first measurement.

Descriptive statistics and Kaplan-Meier plots will be presented for all time to event variables.

The effect of excluding Adjudication Committee-confirmed events from the progression to diabetes endpoint will also be explored; the analysis of this endpoint will parallel the progression to diabetes endpoint analyses:

- Time to progression to diabetes excluding Adjudication Committee-confirmed cases not meeting laboratory test-based definition, i.e., the cases described in Section 3.5.3, Primary endpoint: time to progression to diabetes, (b).

Exploratory analyses will also be performed using general linear models to test each of the two experimental treatments, these include:

- Indices of hyperglycemia
 - Change from baseline at study endpoint in fasting plasma glucose
 - Change from baseline at study endpoint in 2hr post-OGTT plasma glucose value
 - Change from baseline at study endpoint in HbA_{1c}
- Change from baseline in body weight

The covariates in the linear models will be center, baseline value, history of CVD at baseline (yes/no), and the two experimental treatment effects. Small centers may be pooled for the analysis. The exact specification of the pooling algorithm will be defined under blinded conditions. Study endpoint is defined as last post-baseline observation carried forward.

Summary statistics for change from baseline will be presented for the indices of hyperglycemia both at study endpoint and by time period. Time windows will be used to assign study visits to time periods.

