3.5 Visit schedule and assessments

3.5.1 Visit schedule

A minimum of twelve visits are scheduled to be performed in this trial over a period of approximately 72 months. Additional visits will be scheduled as needed (i.e., confirmation of progression of diabetes [refer to Section 3.5.2]).

At Visit 1 (Month –1) subjects will be screened and, if eligible, will enter up to a 4 week treatment-free run-in period. Visit 1 information other than laboratory measurements will be collected using IVRS (for details see Section 3.5.5). Once all results from Visit 1 assessments are available, the investigator will document the decision to randomize or discontinue from screening the subject using IVRS. Randomization will be at Visit 2 (Month 0) and post-randomization visits will be 2 and 4 weeks, 3 and 6 months, and then every 6 months thereafter.

Starting at Visit 2, patient data will be collected using a CRF. Deviations of ± 1 week between the Month 0 and Month 6 visits are acceptable. Deviations of ± 2 weeks between visits at Month 6 and thereafter are acceptable. However, every effort must be made to restore the visit schedule. Since the study duration is dependent on the total number of events reported rather than the individual treatment duration of a specific subject, the follow-up period of 6 years during treatment is an estimate for planning purposes. When the target number of cardiovascular events is reached, all patients will be scheduled to have their final study visit.

Visits will be scheduled between 7:00 AM and 10:00 AM. Patients should be instructed not to take the morning dose of either drug until the visit has been completed. Patient should not eat or drink anything (except water) overnight prior to each scheduled laboratory evaluation. If the patient has not fasted, the collection of laboratory evaluations must be rescheduled to obtain laboratory values in the fasting state.

A summary of evaluations by visit is given in Table 3; details of assessment are given in Sections 3.5.3 to 3.5.5.

Table 3 Evaluation schedule

Examination	S	BL	0.5	1	3	(Visit 6-11)		(visit 11)	(visit 13 onwards)**		Final Visit ^a
						Every 6 months	Every 12 months	Month 36	Every 6 months	Every 12 months	
Informed consent	X										
Inclusion/exclusion criteria	X										
Medical history	X	X									
Concomitant Medications/ Significant Non-drug Therapies	X	X	X	X	X	X		X	X		X
Vital signs	X	X	X	X	X	X	X	X	X	X	X
Physical examination	X						X	X		X	X

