The central (or local) laboratory will use standardized normal value ranges, utilize the same methods and references for methodology and will supply the sponsor with their internal quality control methods and external evaluations of methods and certification.

Laboratory results will be forwarded to the investigator and sponsor for review. The investigator should retain all laboratory results in the patient's source documents.

Notable ranges for selected laboratory tests are provided in Appendix 3.

Hematology

Includes hematocrit, hemoglobin, platelet count, erythrocyte count, total leukocyte count. These parameters will be measured Visit 1 (one measurement must be available prior to randomization), annually thereafter and at the final visit.

Blood chemistry

A fasting venous blood sample will be obtained for analysis of creatinine, SGOT (ALT), SGPT (AST), alkaline phosphatase, LDH, triglycerides, total cholesterol, potassium, sodium, calcium, chloride, BUN, total protein. All tests will be measured at Visit 1 (one measurement must be available prior to randomization), annually thereafter and at the final visit with the exception of LDL and HDL cholesterol which will be measured at Visit 1, Visit 11 (Month 36) and at the final visit, only.

Creatinine and potassium should be measured in patients already receiving an ACE inhibitor or who are initiated on an ACE inhibitor during the course of the study. Creatinine and potassium levels will be assessed at the local laboratory during the initial titration phase at Visit 3 (Week 2) and 4 (Week 4), and after 2 weeks of exposure to the higher dose in the event the patient has his/her initial titration after Visit 3.

Fasting Plasma Glucose (FPG)

FPG will be measured at Visit 1 and at the final visit, respectively (as part of OGTT), and semi-annually from visit 6-11. Thereafter FPG will be measured annually (as part of OGTT).

For patients who have progressed to diabetes and have had an FPG \geq 300 mg/dL (16.7 mmol/L), an annual OGTT is no longer required; an FPG, however, should still be performed. An annual OGTT is still required for all patients with FPG < 300 mg/dL (16.7 mmol/L).

HbA_{1c}

Blood samples for HbA_{1c} will be collected at baseline (visit 2) and at the final study visit. In addition, HbA_{1c} will be measured in subjects with positive, confirmatory OGTT and annually thereafter in patients who have progressed to diabetes.

Urine measurements

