Samples for spot urine albumin and creatinine will be taken at Visit 1 and analyzed for eligible patients, only (one measurement must be available prior to randomization). Following randomization, spot urine albumin and creatinine will be measured annually and at the final visit.

Vital signs

Notable ranges for vital signs are provided in Appendix 3.

Height

Height will be measured at Visit 1.

Pulse rate

Pulse rate will be measured at each visit once in the sitting position after 5 minutes resting followed by one measurement in the standing position after at least 2 minutes of equilibration. Pulse rate will be measured for 30 seconds and before blood pressure measurements.

Blood pressure

Systolic and diastolic blood pressure will be measured at each visit using a validated device (two measurements in the sitting position after 5 minutes resting followed by one measurement in the standing position after at least 2 minutes of equilibration). Blood pressure will be measured by the same clinician using the same device on the patient's dominant arm. The measurements should always be carried out at the same time of the day and prior to the intake of the morning doses.

Body weight

Body weight will be measured to the nearest 0.1 kilogram in indoor clothing but without shoes at each visit using the same scale.

Waist circumference

Waist circumference (the minimum circumference of the waist above the iliac crest) will be measured at Visit 1, yearly thereafter and at the final visit.

Physical examination

A physical examination will be performed at Visit 1, yearly thereafter and at the final visit. Physical examination evaluations should include general appearance, skin, neck (including thyroid), eyes, ears, nose, throat, lungs, heart, abdomen, back, lymph nodes, extremities, and neurological (including sensory) examinations. Information about the physical examination must be present in the source documentation at the study site. Significant findings present prior to randomization will be entered in the Relevant Medical History/Current Medical Conditions Case Report Form at Visit 2. Significant findings made after the start of the study which meet the definition of a pre-defined or serious adverse event (as defined in Section 3.5.4) will be recorded on the Adverse Event Case Report Form.

Electrocardiogram

A standard 12 lead electrocardiogram (ECG) must be obtained at Visit 2, Month 36, and at the final visit.

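### The one-year limit for confirming laboratory renal events equals the annual sampling interval, so the appointment day decides whether the next value confirms an event and when the event is dated

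*Protocol*

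**What the plan says.** Protocol Section 6.1.5.2 lists three exploratory renal time-to-event analyses, and each has a laboratory component that needs a second value:

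- New microalbuminuria: "microalbuminuria is defined as urine albumin/creatinine ratio > 30 mg/g, confirmed by a second measurement".
- Progression to macroalbuminuria: "urine albumin/creatinine ratio > 300 mg/g, confirmed by a second measurement".
- The renal composite: "Time to two-fold increase from baseline in serum creatinine (confirmed by a second measurement"), together with end-stage renal disease and renal death, which need no second value.

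The section then sets the limit: "Confirmatory measurements for renal function related variables must take place within one year after the first measurement".

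Section 3.5.4 fixes when the samples are taken. For urine: "Following randomization, spot urine albumin and creatinine will be measured annually and at the final visit". For chemistry, which includes creatinine: "All tests will be measured at Visit 1 (one measurement must be available prior to randomization), annually thereafter and at the final visit". Table 3 agrees.

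Section 3.5.1 gives the tolerance, "Deviations of ± 2 weeks between visits at Month 6 and thereafter are acceptable", and adds "However, every effort must be made to restore the visit schedule".

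**The concern.** The limit is the same length as the nominal gap between two samples. With a two-week tolerance on each visit, the next scheduled value falls on one side of the limit or the other for reasons unrelated to the kidney. A value on day 358 confirms and a value on day 372 does not, although both visits may be fully compliant.

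No other source of confirming values is specified. The additional visits in Section 3.5.1 are explained by confirmation of diabetes. The extra local creatinine tests in Section 3.5.4 cover only patients on ACE inhibitors around titration. For diabetes, by contrast, Section 3.5.3 orders a repeat test, states its limit in days, and lets the adjudication committee take repeats that come too late. The renal endpoints have a mandatory limit and none of these provisions.

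At stake are the number and timing of events in the renal analyses. These use the discrete-time model on yearly samples, so one missed confirmation moves an event by a whole interval.

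**Working it through.** The protocol gives no event count, power or visit-timing distribution for these endpoints, so there is no stated figure to reproduce.

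**Inputs.** Limit: one year, read as 365 days (6.1.5.2). Nominal gap between samples: 12 months (3.5.4, Table 3). Visit deviation: ±14 days (3.5.1). Assumptions: deviations at different visits are independent and share one distribution, uniform over the 29 allowed days in the base case. The section does not say how a renal event is dated; I take the first value of the pair that qualifies, as Section 3.5.3 does for diabetes.

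**1. Range of compliant gaps.** 365 − 14 − 14 = 337 days to 365 + 14 + 14 = 393 days. Reading the tolerance as ±14 days on each of two six-month intervals gives the same range.

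**2. One pair of annual values.** Gap = G + d2 − d1, where G is the nominal gap and d1, d2 are the deviations. The difference d2 − d1 is symmetric about zero whatever the shape of the distribution. So for G = 365, P(gap > 365) = (1 − P(tie))/2. Uniform case: (1 − 1/29)/2 = 48.3%.

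| Deviations | G = 364 (52 weeks) | G = 365 | G = 366 |
|---|---|---|---|
| Uniform ±14 days | 44.9% | 48.3% | 51.7% |
| Truncated normal, SD 7 | 43.5% | 47.8% | 52.2% |
| Truncated normal, SD 5 | 41.5% | 47.2% | 52.8% |
| Truncated normal, SD 3 | 36.2% | 45.3% | 54.7% |
| Truncated normal, SD 2 | 29.7% | 42.9% | 57.1% |
| Skewed to late visits | 39.5% | 46.2% | 53.8% |
| 40% exactly on the day | 38.4% | 41.4% | 58.6% |

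The last column applies only to an interval containing a leap day with the limit still counted as 365 days. With a 366-day limit, the uniform figure there returns to 48.3%.

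**3. A persistent abnormality.** The value is measured again every year, so one failed pair is not the end. With G = 365, a gap exceeds the limit exactly when d2 > d1. Hence m successive gaps all fail only if m + 1 deviations are strictly increasing: P(m) = C(29, m+1)/29^(m+1).

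- m = 1: 406/841 = 48.3%
- m = 2: 3,654/24,389 = 15.0%
- m = 3: 3.4%
- m = 4: 0.6%

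**4. With a final-visit sample.** Suppose there are K annual visits, first positives are equally likely at each, and the final visit comes within a year of the last annual one, so that this last pair always qualifies.

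- Share dated a year or more late = 48.3% × (K − 1)/K: 38.6% for K = 5 and 42.2% for K = 8.
- Mean delay over all first positives = average over visits of P(1) + … + P(m), with m the remaining annual gaps. For K = 5: (0.672 + 0.666 + 0.633 + 0.483 + 0)/5 = 0.49 year. For K = 8: (3 × 0.673 + 0.672 + 0.666 + 0.633 + 0.483 + 0)/8 = 0.56 year.
- Never confirmed: almost none.

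**5. Without a final-visit sample.** Among first positives with at least one further annual value, the share never confirmed is the average of P(m):

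- K = 5: (0.483 + 0.150 + 0.034 + 0.006)/4 = 17%.
- K = 8: (0.483 + 0.150 + 0.034 + 0.006 + 0.001)/7 = 10%.

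The risk sits with late first positives: 48% when one further annual value remains, 3.4% when three remain.

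**6. Effect of a wider limit** (uniform, G = 365). At one year plus one window (379 days), 12.5% of compliant next-annual values still fail. At one year plus both windows (393 days), none do.

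**The case against.** The strongest reply is that the protocol does not mean day 365. Where it wants a day count it gives one, as for the diabetes repeat test. The renal analyses use a discrete-time model, and with annual sampling the natural sense of the rule is the next annual visit. Turning that into days could be left to the SAP, which is not at hand. This is a fair account of what was probably intended. But the sentence is mandatory, limits the time from the first measurement, and names no visit. A programmer who applies it literally gets the results above.

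A second reply is that the size depends on visit behaviour that the protocol does not describe. That stands: the share is an assumption with a range, and tight 52-week scheduling brings it down to about 30%.

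Three stronger readings are tempting, and the documents do not support them:

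- A reader might infer that about half of all persistent renal events are discarded. The 48% is the failure rate of a single pair. Later annual pairs usually confirm, and the final visit, which includes both urine and chemistry, can confirm a value from the last annual visit.
- A reader might infer a biased treatment comparison. Visits are scheduled under double-blind conditions and the rule is the same in every arm; nothing in the protocol points to a differential effect.
- A reader might infer harm to the main conclusions. These are exploratory analyses, so no primary test, alpha level or sample size is involved. End-stage renal disease and renal death are untouched.

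Unscheduled repeats are not forbidden either, but none is specified.

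**Conclusion.** The point holds as a mismatch between the confirmation rule and the sampling schedule. Compliant next-annual values fall on both sides of a 365-day limit. With uniform deviations and a nominal gap of 364 to 366 days, about 45% to 52% of them are rejected; with tight 52-week scheduling, about 30%.

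For persistent abnormalities the consequence is mainly later dating. About 39% to 42% of first positives shift by a year or more, and the mean delay over all first positives is about half a year. This assumes five to eight annual visits, first positives spread evenly over them, and a final visit within a year of the last annual one. Outright loss is limited mainly to late first positives in patients who die or miss the final visit: about 10% to 17% go unconfirmed if there is no final-visit sample.

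The effect should be similar across arms and touches exploratory endpoints only. It costs precision and accuracy of timing. It is still worth correcting, because the rule makes event status and date depend on the appointment day and the remedy is nearly free.

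**What to change.** Replace the one-year sentence in Section 6.1.5.2, or settle it in the SAP before unblinding, with:

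*Renal laboratory events must be confirmed at the next scheduled annual or final measurement, allowing for the visit windows (no more than one year plus 4 weeks, 393 days, after the first). The event is dated at the first value.*

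The 393 days follow from the protocol's own windows: 365 + 2 × 14. A calendar year plus 4 weeks also covers an interval with a leap day.

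The cost is one sentence; no samples or visits are added. The downside is that values confirmed slightly later than 365 days are accepted.
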